2.1.1.2 Study Day 1 and other study days

The first day of administration of randomized study treatment (first dose) is defined as Study Day 1 or Day 1.

All other study days will be labeled relative to Day 1. For event dates on or after Day 1, study day for a particular event date is calculated as [Date of event] – [Date of first dose] +1, i.e., Day 2, Day 3, etc., will be one day, two days, etc., after Day 1, respectively. For the dates before Day 1, study day for an event date is calculated as [Date of event] – [Date of first dose], i.e., Day -1, Day -2, etc., will be one day, two days, etc., before Day 1, respectively. Duration of an event will be calculated as (Event end date – Event start date + 1).

The descriptor “Day 0” will not be used.

2.1.1.3 Screening, baseline and post-baseline definitions

Screening refers to any procedures (e.g., checking inclusion and exclusion criteria) performed prior to the date of first dose of study treatment. Per protocol, subject informed consent must be obtained prior to performing any study related activity. The date of signing informed consent is the start date of screening period. Any assessment obtained during the screening period will be labeled screening assessment. Assessments made on Day 1 may occur before or after the randomization or the first dose. Further information will be found in Programming Datasets Specifications (PDS).

In general, a baseline value refers to the last measurement made prior to administration of the first dose of study treatment. A post-baseline value refers to a measurement taken after the first dose of study treatment. However, for vital sign, laboratory assessments and ECG if no pre-treatment value exists, values obtained after first dose of treatment can be used as baseline only if it was collected on the same day as first dose.

Of note, baseline will be derived based on the first dose day while exact dosing time is not considered.

2.1.1.4 Day of last dose of randomized study treatment

The date of last dose will be collected via the electronic case report form (eCRF). The subject’s exposure will be calculated considering the end of study visit (e.g., study completion visit). If a subject discontinued early, then the last dose + 84 days or the last visit during the follow-up period whichever occurs earlier is considered.

2.2 Analysis sets

The following analysis sets will be used in this study:

Randomized set: The randomized set will be defined as all participants who were randomized. Unless otherwise specified, mis-randomized participants (mis-randomized in IRT) will be excluded from the randomized set.

Mis-randomized participants are defined as those participants who were mistakenly randomized into the IRT prior to the site confirming all eligibility criteria had been met and to whom no study medication was given. Mis-randomized participants are treated as screen failures.

Full analysis set (FAS): The FAS will be comprised of all participants from the randomized set to whom study treatment has been assigned. Following the intent-to-treat principle, participants will be evaluated according to the treatment assigned to at randomization, but actual stratum, if stratified randomization is used.

Safety set: The safety set includes all participants who took at least one dose of study treatment during the treatment period. participants will be evaluated according to treatment received.

2.2.1 Subgroup of interest

The primary endpoint will be evaluated within TNF α naïve patients using the stratification subgroups (CRP+/MRI+, CRP+/MRI-, CRP-/MRI+). The analysis will be performed using a logistic regression model as specified in [Section 5.5.1.1](#).

2.3 Patient disposition, demographics and other baseline characteristics

2.3.1 Patient disposition

The number of participants screened will be presented. In addition, the reasons for screen failures will be provided. The number and percentage of participants in the randomized set who completed the study periods and who discontinued from treatment or study prematurely (including the reason for discontinuation) will be presented at the end of each treatment period (e.g. Week 16, and entire treatment period), if appropriate, for each treatment group and all participants.

For each protocol deviation (PD), the number and percentage of participants for whom the PD applies will be tabulated by initial randomized treatment groups on the Randomized set population.

2.3.2 Demographics and baseline characteristics

The following common background and demographic variables will be summarized:

Continuous variables:

- Age
- Height
- Weight
- Body mass index (BMI) = (body weight in kilograms) / (height in meters)²

Categorical variables:

- Age categories (<45 years, 45 years and older)
- Gender
- Race
- Ethnicity
- Smoking status at baseline

Baseline disease characteristics will also be summarized for the following variables:

- Participant's global assessment of disease activity and other ASAS components, hsCRP (mg/L and > ULN), ESR (mm/h), prior use (yes/no) of TNF- α inhibitors, use (yes/no) and separate NSAIDs (yes/no) and dose of concomitant NSAIDs, MTX (yes/no) and MTX (mg/week), susulfasalazine (yes/no) and sulfasalazine (g/day) and systemic corticosteroids (yes/no) and systemic corticosteroids (mg/day) at randomization, time since first diagnosis of nr-axSpA and time since onset of inflammatory back pain(years), HLA-B27, [REDACTED], total back pain (VAS), nocturnal back pain (VAS), total BASDAI score, spinal pain (BASDAI question #2), total BASFI score, [REDACTED], [REDACTED] and each randomization strata level (CRP+/MRI+, CRP-/MRI-, CRP+/MRI-).

Unless otherwise specified, summary statistics will be presented for continuous variables for each treatment group and for all subjects (total) in the randomized set. The number and percentage of subjects in each category will be presented for categorical variables for each treatment group and all subjects (total) in the randomized set.

Unless otherwise specified, analyses will be based on the randomized set.

2.3.3 Medical history

A history of nr-axSpA with focus on previous extra-articular involvement and past therapies for nr-axSpA will be obtained and summarized by treatment group for all patients in the randomized set. Any other significant prior or active medical condition at the time of signing informed consent will be recorded and coded using the MedDRA dictionary. These medical conditions will be summarized by primary system organ class and preferred term.

To establish a BSL level of cardiovascular risk, the number and percentage of participants with pre-solicited cardiovascular risk factors will be summarized by treatment group. The number of cardiovascular risk factors that each participant has will also be summarized by treatment group. If it is unknown whether a participant currently or previously experienced a specific cardiovascular risk factor, it will be assumed that cardiovascular risk factor did not occur for that participant.

Unless otherwise specified, analyses will be based on the randomized set.

2.4 Treatments (study treatment, rescue medication, concomitant therapies, compliance)

2.4.1 Study treatment / compliance

The analysis of study treatment data will be based on the safety set. The number of active and placebo injections will be presented by treatment group.

The duration of exposure to study treatment will also be summarized by treatment group. In addition, the number and percentage of participants with cumulative exposure levels (e.g. any exposure, ≥ 1 week, ≥ 2 weeks ≥ 3 weeks, ≥ 4 weeks, ≥ 8 weeks, etc.) will be presented.

Duration of exposure is defined as the time from first dose of study treatment to the time of treatment switch (for participants who switch treatment) or minimum of (last dose of the treatment + 84 days) and (last visit date). Participants who switch treatment during the study (e.g. from placebo to active treatment) will have exposure to both medications using the appropriate start and stop dates.

Duration of exposure (years) = duration of exposure (days) / 365.25

Duration of exposure (100 subject years) = duration of exposure (years) / 100

The analysis of duration of exposure described above will be done for the entire study treatment period.

2.4.1.1 Visit window

Analysis visit windows will be used for the data that is summarized by visit; they are based on the study visit and evaluation schedule and comprise a set of days around the nominal visit day. For any assessment, there are protocol defined scheduled visits around which analysis visit windows were created to cover the complete range of days within the study.

When visit windows are used, all visits will be re-aligned, i.e., they will be mapped into one of the visit windows. E.g., if the Week 4 visit of a subject is delayed and occurs on Day 46 instead of on Day 29, it will be re-aligned to visit window Week 8. In the case of major deviations from the visit schedule, or due to unscheduled visits, several assessments of a subject may fall in a particular visit window (either scheduled or unscheduled). Statistical approaches to handle multiple assessments in a given visit window are specified below.

As for the Week 60 (follow-up) visit, only assessments that come as nominal Week 60 visit will be directly assigned as Analysis Week 60 visit. Other assessments that are beyond the last on-treatment visit window (Week 52) won't be mapped to any analysis visit. Of note, subjects are allowed to have gaps in visits.

Table 2-1 Analysis visit windows

| Analysis visit | Target Day | Group 1 | Group 2 | Group 3 | Group 4 | Group 5 | Group 6 |
|----------------|------------|----------|----------|----------|----------|----------|----------|
| Baseline | 1 | ≤ 1 | ≤ 7 |
| Week 1 | 8 | 2-11 | 2-11 | | | | |
| Week 2 | 15 | 12-18 | 12-22 | | | | |
| Week 3 | 22 | 19-25 | | | | | |

| | | | | | | | |
|---------|-----|---------|---------|---------|---------|---------|---------|
| Week 4 | 29 | 26-43 | 23-57 | | | | |
| Week 8 | 57 | 44-71 | | 2-85 | 2-85 | | |
| Week 12 | 85 | 72-99 | 58-99 | | | | |
| Week 16 | 113 | 100-127 | 100-155 | 86-141 | 86-239 | 2-239 | 8-239 |
| Week 20 | 141 | 128-155 | | | | | |
| Week 24 | 169 | 156-183 | 156-169 | 142-225 | | | |
| Week 28 | 197 | 184-211 | 170-239 | | | | |
| Week 32 | 225 | 212-239 | | | | | |
| Week 36 | 253 | 240-267 | | | | | |
| Week 40 | 281 | 268-295 | 240-323 | 226-323 | | | |
| Week 44 | 309 | 296-323 | | | | | |
| Week 48 | 337 | 324-351 | | | | | |
| Week 52 | 365 | 352-379 | 324-379 | 268-379 | 240-435 | 240-379 | 240-435 |

*The first administration of randomized study treatment (first dose) is defined as Day 1.

Group 1: Patient's global assessment of disease activity (VAS), Patient's assessment of back pain intensity (VAS), BASFI, BASDAI, [REDACTED], hsCRP, Vital signs

Group 2: Hematology, blood chemistry, urinalysis

Group 3: ASQoL, SF-36, [REDACTED]

Group 4: Lipids

Group 5: Weight, ECG

Group 6: MRI

The following rules are used to determine the window for an applicable visit post baseline “Lower limit”=“upper limit of prior applicable visit”+1. “Upper limit”=“target day of current visit”+ integer part of (“target day of next applicable visit”-“target day of current visit”)/2. Lower limit of the first applicable visit is always Day 2. Day 1 is the date of the first dose of randomized study treatment.

The mapping described above applies to all visits (not just scheduled visits). Repeat and/or unscheduled visits (which will be numbered in the database according to new NCDS standards) will be mapped for analysis purposes in the same way as scheduled visits. This leaves the possibility, then, for multiple measurements within an analysis window. If more than one assessment falls into the interval, the rules defined in [Section 2.4.1.2](#) are applied.

The analysis visit will be used for listing of visit and period for safety data. If a visit falls after the last visit window, it is not assigned an analysis visit and will be listed under label “After Week 60”.

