### **3 Study design**

This is a randomized, double-blind, placebo-controlled study of secukinumab 150 mg s.c. to evaluate the safety, tolerability and efficacy in Chinese participants with active non-radiographic axial spondyloarthritis (nr-axSpA).

A screening period of up to 10 weeks before randomization will assess participant eligibility, followed by 16 weeks of double blind treatment period and 44 weeks open label period.

Approximately 134 participants will be randomized in a ratio of 1:1 to receive secukinumab 150 mg s.c. or placebo:

- Group 1: secukinumab 150 mg (1 mL, 150 mg/mL) s.c. pre-filled syringe (PFS) at baseline (BSL), Weeks 1, 2, and 3, followed by administration every four weeks starting at Week 4
- Group 2: placebo (1 mL) s.c. PFS at BSL, Weeks 1, 2 and 3, followed by administration every four weeks starting at Week 4

Participants will be stratified at randomization according to the subgroup of objective signs of inflammation they belong to (based on their CRP and MRI status at screening: CRP+ and MRI+, CRP+ and MRI-, CRP- and MRI+).

Additionally, it is planned to enroll no more than approximately 10% Tumor Necrosis Factor - Inadequate Response (TNF $\alpha$ -IR) participants in the study.

The primary analysis will be performed after all participants complete Week 16 visit to support registration in China.

[figure not shown]
From Week 16, all participants will switch to open label secukinumab 150 mg s.c., including all placebo participants. The first dose of open label secukinumab 150 mg s.c. should start at the Week 16 visit, only after performing all assessments for that visit. However, all participants and investigators/site staff will remain blinded to the original randomized treatment group assignment (150 mg vs placebo).

At week 24, non-responders (defined as not achieving ASAS20) will be escalated to secukinumab 300 mg s.c. Responders will continue secukinumab 150 mg s.c. treatment.

Study treatment will continue up to Week 48.

An end of treatment visit will be performed 4 weeks after last study treatment administration i.e. at Week 52 and a post treatment follow-up visit is to be done 12 weeks after last study treatment administration for all participants (regardless of whether they complete the entire study as planned or exit the study early).

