## 6.5 Dose escalation and dose modification

Study treatment dose adjustments are not permitted. Study treatment interruption is also not permitted with the following exceptions:

Study treatment interruption is only permitted if, in the opinion of the investigator, a participant is deemed to be placed at a significant safety risk unless dosing is temporarily interrupted. In such cases study treatment should be interrupted only during the time that this risk is present and ongoing. Study treatment can be restarted at the next scheduled visit after resolution of the safety risk.

The effect of secukinumab on live vaccines is unknown; therefore, live vaccines should not be administered during participation in the study. In case a live vaccine has been administered due to a medical urgency, the participant must discontinue the study treatment.

Any study treatment interruption must be recorded on the Dosage Administration Record eCRF.

In all cases the **original visit schedule should be maintained** (no recalculation from the last visit).

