## 8 Visit schedule and assessments

The Assessment Schedule [Table 8-1](#) lists all of the assessments and when they are performed.

Participants should be seen for all visits/assessments as outlined in the assessment schedule [Table 8-1](#) or as close to the designated day/time as possible. Missed or rescheduled visits should not lead to automatic discontinuation.

Participants who prematurely discontinue study should return for end of treatment visit 4 weeks after the last study treatment administration, as well as return for the follow-up visit 12 weeks after the last study treatment administration.

If they refuse to return for these assessments or are unable to do so, every effort should be made to contact them or a knowledgeable informant by telephone to determine the reason.

At a minimum, participants will be contacted for safety evaluations during the 30 days following the last study visit, however preferably for a follow-up visit 12 weeks after last study treatment. Attempts to contact the participant should be recorded in the source documentation.

If a global health disruptive event, such as a pandemic/epidemic (e.g. COVID-19) limits or prevents on-site study visits, study treatment dispensing and other study assessments may be impacted. The instructions and procedures of this situation are outlined in [Section 16.9](#).

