| Post-baseline efficacy | All data | 
For visits without switch of treatment in the window, the measurement closest to the target will be used. In the event two measurements are taken equally apart (e.g. 1 before target date and 1 after) the first one will be used.
 
For visits during which the patient switchers from placebo to AIN the following will be done based on whether the patient met the rescue criteria:
 
 if the analysis visit window is \leq week 16, then 
 - if available, the closest measurement to the target date which is ON or BEFORE the switch date will be used (i.e. the closest measurement to target which is on placebo) - if there are no data on or before the switch then the closest measurement to the target date after the switch will be used if the analysis visit window is $>$ week 16, then 
 - if available, the closest measurement to the target date which is AFTER the switch date will be used (i.e. the closest measurement to target which is on AIN) - if there are no data AFTER the switch then the closest measurement to the target date before the switch will be used 
Cases where the same parameter is recorded more than once on the same date will be handled as follows:
 
* if time of completion exists the earliest measurement will be used;
 |

| | | |
|----------------------|---|---|
| | | * if time does not exist the measurement from the lowest CRF visit number will be used |

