2.5.3 Handling of missing values/censoring/discontinuations

Missing data for ASAS40 response for data up to Week 16 will be handled as follows:

1. Participants who discontinue from treatment or study for any reason will be considered as non-responders from the time of discontinuation through Week 16
2. Participants who do not have the required data to compute responses (i.e., ASAS components) at BSL and at the specific timepoint will be classified as non-responders at the specific timepoint.

Participants who are unblinded prior to the scheduled time point will be considered non-responders from the time of unblinding up to Week 16.

The primary analysis will use the non-responder imputation.

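### A Week 16 visit held on Day 128 or later is relabelled by study day, so an observed pre-switch ASAS40 outcome is normally scored as non-response

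*SAP*

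**What the plan says.** **Mapping.** SAP 2.4.1.1 states: "When visit windows are used, all visits will be re-aligned, i.e., they will be mapped into one of the visit windows". Its illustration is that "if the Week 4 visit of a subject is delayed and occurs on Day 46 instead of on Day 29, it will be re-aligned" to the Week 8 window. The section says that the mapping covers scheduled as well as unscheduled visits. The one exception is the follow-up visit: "only assessments that come as nominal Week 60 visit will be directly assigned as Analysis Week 60 visit".

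**Windows.** SAP Table 2-1 puts patient global assessment, back pain, BASFI, BASDAI and hsCRP in Group 1. There Week 16 (target Day 113) is Days 100–127, Week 20 is Days 128–155 and Week 24 starts on Day 156. For ASQoL and SF-36 (Group 3) Week 16 is Days 86–141. For MRI (Group 6) it is Days 8–239.

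**Selection within a window.** Under SAP 2.4.1.2 a responder variable built on quantitative components takes the visit assigned to those components. Table 2-2 takes the value closest to target. For a placebo participant who switches in a window after Week 16, "the closest measurement to the target date which is AFTER the switch date will be used" where there is one.

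**Missing data.** Under SAP 2.5.3, participants without the data needed at baseline and at the timepoint are "classified as non-responders at the specific timepoint".

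**Protocol timing.** Section 3 says the first open-label dose "should start at the Week 16 visit, only after performing all assessments for that visit". Section 8 asks for visits as close to the scheduled day as possible and adds: "Missed or rescheduled visits should not lead to automatic discontinuation". Section 6.5 says that the "original visit schedule should be maintained".

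**The concern.** The blinded period ends at a visit, not on a calendar day. A participant who attends Week 16 late is still assessed on randomized treatment, before any open-label drug. The primary variable in SAP 2.5.1 combines staying in the study and on randomized treatment through 16 weeks with achieving ASAS40. A late attender with an ASAS40 response can meet both parts and still be counted as a failure, because the study day moved the value out of the Week 16 window.

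This is an estimation study whose result is judged by how much of the global treatment difference it retains. Replacing observed responses with imputed failures changes the quantity being reported. Late visits are foreseeable: the protocol tolerates rescheduling, and its pandemic appendix (16.9, Visits) does not allow remote replacement of visits up to and including Week 16, so a participant kept from the site must postpone or miss the visit.

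**Working it through.** **1. Reproduce the windows.** Inputs: the formula in SAP 2.4.1.1 and target days 85, 113, 141 and 169 from Table 2-1. Upper limit = target + integer part of (next target − target)/2. Lower limit = previous upper limit + 1.
- Week 12 ends on 85 + 28/2 = Day 99.
- Week 16 runs from Day 100 to 113 + 28/2 = Day 127.
- Week 20 runs from Day 128 to 141 + 28/2 = Day 155.

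These match Table 2-1, and the SAP's Day 46 example also lands in Week 8. A visit 14 days late (Day 127) is Week 16. One 15 days late (Day 128) is Week 20, and from Day 156 it is Week 24.

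**2. Follow a nominal Week 16 visit on Day 130.**
- All assessments precede the open-label dose given that day.
- The four ASAS40 domains are labelled Week 20, and ASAS40 follows them.
- Days 100–127 hold no other scheduled target day. The window is filled only by an unscheduled assessment or by a Week 12 visit at least 15 days late (85 + 15 = 100).
- Otherwise the participant is a non-responder under SAP 2.5.3.
- In the Week 20 window, a placebo participant's Day 130 value gives way to any post-switch value. A secukinumab participant's Day 130 value is 11 days from target, so an on-time Day 141 visit displaces it. It is kept if the next visit is missed or falls on Day 152 or later (152 − 141 = 11, and ties go to the earlier value).

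**3. The same Day 130 visit in other groups.** It is Week 16 for SF-36 and ASQoL (86–141) and for MRI (8–239), but Week 20 for ASAS40, BASDAI, BASFI and hsCRP.

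**4. Size.** Inputs from SAP 3.1: response 41.5% and 29.2%, 60 TNF-naive participants per arm. The exact difference of two Binomial(60, p) variables gives P(difference > 6.15 points) = 77.3% and P(difference > 0) = 90.7%, as the SAP states.

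Assume a share f of an arm is reclassified, unrelated to response. Each rate becomes p × (1 − f). At 5% in both arms: 0.415 × 0.95 − 0.292 × 0.95 = 0.39425 − 0.2774 = 0.117.

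| f secukinumab | f placebo | Expected difference (points) | P(> 6.15) | P(> 0) |
|---|---|---|---|---|
| 0 | 0 | 12.3 | 77.3% | 90.7% |
| 2% | 2% | 12.05 | 76.5% | 90.3% |
| 5% | 5% | 11.7 | 75.4% | 89.8% |
| 10% | 10% | 11.1 | 73.3% | 88.7% |
| 5% | 0 | 10.2 | 69.6% | 86.2% |
| 10% | 0 | 8.15 | 60.7% | 80.4% |
| 0 | 5% | 13.8 | 82.2% | 93.3% |

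One reclassified responder moves an arm by 1/60 = 1.67 points.

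**The case against.** The windows are a pre-specified convention. They follow a stated formula, run from 13 days before to 14 days after Day 113, and apply equally to both arms. A value on Day 128 comes 128 − 85 = 43 days after an on-schedule Week 12 dose, under four-weekly dosing, so declining to call it Week 16 is defensible. The protocol points to few such visits, there is no hypothesis test to lose, and Week 60 is a weak precedent because its study day varies by design. Protocol 12.4.4 also lists multiple imputation and observed-data analyses as possible alternatives.

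Much of this stands. It bears on frequency and on the need for an upper limit. It does not explain why an observed blinded outcome should be replaced by an imputed failure when the SAP accepts the same visit as Week 16 for SF-36 and ASQoL. The alternative analyses, as far as they are visible, would still treat the real value as missing at Week 16.

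A reader might infer more than the documents support:
- **That the late value is never used.** It can serve as Week 20 when nothing else is preferred there.
- **That the participant is always a non-responder.** Another complete assessment on Days 100–127 prevents this.
- **That late attenders leave the BASDAI, BASFI and hsCRP analyses.** In those mixed models (SAP 2.6.3) only the Week 16 value is lost; other visits still contribute.
- **That the estimate is known to be biased by a material amount.** No lateness rate is given, overall or by arm.

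**Conclusion.** The point holds as a gap in the derivation of the primary endpoint. For a nominal Week 16 visit at least 15 days late, the SAP's rules normally turn an observed, pre-switch ASAS40 outcome into a non-response, and they treat the same visit differently across endpoints.

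The effect is small if such visits are rare and balanced: about 0.6 points off the expected difference at 5% in each arm. It grows, in either direction, if lateness differs by arm. These figures assume that lateness is unrelated to response and that no other assessment fills the window. The shares are illustrations, not estimates. The change is worth making because it is cheap and concerns the primary endpoint.

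**What to change.** In SAP 2.4.1.1 add for Group 1: the Week 16 analysis value is the nominal Week 16 assessment if it was made before the first open-label dose, before discontinuation of study treatment, and no later than Day 141; otherwise the Day 100–127 window applies. Day 141 is the upper limit that the SAP already uses for Week 16 in Group 3. A value used as Week 16 should not also be a candidate for Week 20.

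Report the number of nominal Week 16 visits outside Days 100–127 by arm, and run the primary analysis with both rules.

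Timing matters. The SAP's document history marks the Amendment 2 changes as made before the Week 52 lock, which suggests, without saying so, that the Week 16 lock may have passed. Protocol 6.4 unblinds sponsor staff, except field monitors, at the primary analysis. If the lock has passed, keep the day-based analysis as primary and report the nominal-visit analysis as supportive.

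The cost is one SAP rule, a small programming change and one extra run. The downside is that a few Week 16 values will come more than six weeks after the Week 12 dose (up to 141 − 85 = 56 days for an on-schedule dose); the paired analysis makes their influence visible. Visits after Day 141 would still be handled by study day.

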2.4.1.2 Multiple assessments within visit windows

When there are multiple assessments in a particular visit window, the following rules are applied to select one value “representing” the subject in summary statistics in a visit window (See [Table 2-2](#)).

The definition of baseline assessment is included in [Section 2.1.1.3](#). For post-baseline visit windows the following applies (unless otherwise specified):

- for *quantitative variables*, the *closest* to the actual visit is chosen (if two assessments have the same distance, then the earlier one will be chosen),

- for *qualitative variables*, the *worst* record is selected. It is noted that in the analyses performed, *worst* case is always well defined (e.g., for urine protein values “+” and “++”, the worst case is defined as “++”),
- in case qualitative variables are based on quantitative variables, e.g. BASDAI50, the visit will be assigned to the quantitative variable, and this visit will be used for the derived qualitative variable.

Table 2-2 Rules for selecting values for analysis within a given visit window

| Timing of measurement | Type of data | Rule |
|------------------------|--------------|---|
| Baseline | All data | 
The last non-missing measurement made prior to or on the date of administration of the first dose of study treatment (the reference start date / Day 1). If a patient did not receive any dose of study treatment, then the randomization date will be used. Only date part is considered if just one assessment on Day 1.
 
If there are multiple assessments on Day 1, following rules will apply:
 
 If assessment time exists, 
 * select the last available measurement prior to reference start date/time considering time; * if no measurement prior to reference start date/time considering time, select the earliest measurement post reference start date/time considering time. If assessment time does not exist, select the available measurement from the lowest CRF visit number. 
For MRI, a baseline value is the last measurement prior to dosing if available. Otherwise, take the first value within 7 days post dosing.
 |

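### SAP Table 2-1 departs from its own window rule: Group 3 Week 52 overlaps Week 40, and no visit schedule yields the Group 2 Week 16, 24 and 28 windows together

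*SAP*

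**What the plan says.** SAP Section 2.4.1.1 realigns every visit for by-visit summaries: "they will be mapped into one of the visit windows". Below Table 2-1 it gives the construction rule. A window starts one day after the "upper limit of prior applicable visit". It ends at the target day plus the integer part of half the gap to the next applicable target day. The first window starts on Day 2. No exception is stated for Group 2 (hematology, blood chemistry, urinalysis) or Group 3 (ASQoL, SF-36 and a redacted item).

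The relevant rows of Table 2-1 are:

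- Week 24, Groups 1 to 3: "156-183 | 156-169 | 142-225"
- Week 40, Groups 1 to 3: "268-295 | 240-323 | 226-323"
- Week 52, Groups 1 to 4: "352-379 | 324-379 | 268-379 | 240-435"

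Group 2 is also printed as 100-155 at Week 16 and 170-239 at Week 28.

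Section 2.4.1.2 then chooses among several values in one window. The by-visit efficacy and safety rules in Table 2-2 begin: "For visits without switch of treatment in the window, the measurement closest to the target will be used". There is a separate branch for windows in which a participant switches from placebo to active drug. Notable abnormalities take the most extreme value in the window. The text above the table adds: "for *qualitative variables*, the *worst* record is selected".

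**The concern.** A table that programmers will follow literally should agree with the rule printed under it.

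In Group 3, a questionnaire completed on its Week 40 target (Day 281) belongs to both Week 40 and Week 52. Section 2.4.1.2 settles several values in one window; it does not settle one value in two windows.

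In Group 2, the Week 24 window closes on its own target day. If Week 24 is a laboratory visit, a sample taken 1 to 14 days late (Days 170-183) is labelled Week 28, and one taken on Days 142-155 is labelled Week 16.

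Two programmers, one working from the rule and one from the table, would produce different Week 16, 24 and 28 laboratory summaries and different Week 52 questionnaire summaries.

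**Working it through.** **Inputs.** All come from SAP Section 2.4.1.1: the window rule, the target days (Week *w* = Day 7*w* + 1), and the filled cells of each column, read as that group's applicable visits. Two conventions are needed. Week 52 upper limits are taken as printed, because the Week 60 visit is assigned by its nominal label and there is no next window. The Group 6 (MRI) start on Day 8 is taken from its baseline window of up to Day 7.

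**Formula.** upper(i) = T(i) + int[(T(i+1) − T(i))/2]; lower(i) = upper(i−1) + 1.

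**What reproduces.** Every cell in Groups 1, 4, 5 and 6. In Group 2, Weeks 1, 2, 4, 12, 40 and 52. In Group 3, Weeks 8, 16, 24 and 40.

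**Group 3**

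- Week 24: 169 + int(112/2) = 225, as printed. This limit requires Week 40 to be the next visit.
- Week 40: 281 + int(84/2) = 323, as printed.
- Week 52 must therefore start at 323 + 1 = 324. The table prints 268.
- Overlap: 323 − 268 + 1 = 56 days.
- 268 does follow from the rule if Week 40 is not a visit: 169 + int(196/2) = 267, plus 1. In that case Week 24 would have to end at 267, not 225, and there would be no Week 40 cell. The column is inconsistent under either schedule.

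**Group 2**

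| Visit | Target | Rule | Printed |
|---|---|---|---|
| Week 16 | 113 | 100 to 113 + int(56/2) = 141 | 100-155 |
| Week 24 | 169 | 142 to 169 + int(28/2) = 183 | 156-169 |
| Week 28 | 197 | 184 to 197 + int(84/2) = 239 | 170-239 |

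Four limits differ: the Week 16 upper, both Week 24 limits and the Week 28 lower. An upper limit of 155 follows if Week 24 is not a visit (113 + int(84/2) = 155), but then Week 24 should have no cell and Week 28 should be 156-239. An upper limit of 169 for Week 24 needs int[(next − 169)/2] = 0, which means a next visit on Day 170.

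**Could another schedule explain it?** All 65,535 non-empty subsets of the 16 post-baseline visits were tried. None gives the three Group 2 windows together, and none gives 156-169 for Week 24 even alone. Week 16 as 100-155 and Week 28 as 170-239 can each arise singly, under different schedules.

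**How far the displaced days lie from their assigned target**

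| Assigned visit | Displaced days | Distance (days) | Competing days | Distance (days) |
|---|---|---|---|---|
| Group 3 Week 52 (Day 365) | 268-323 | 42-97 | 324-379 | 0-41 |
| Group 2 Week 16 (Day 113) | 142-155 | 29-42 | 100-141 | 0-28 |
| Group 2 Week 28 (Day 197) | 170-183 | 14-27 | 184-210 | 0-13 |

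Under closest-to-target selection, a displaced value is used only when no competing value exists.

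**The case against.** The mismatch itself is hard to dispute; the case on the other side concerns how much it matters.

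- **Selection rules protect the result.** This largely stands. A misplaced value normally loses to one nearer the target. For placebo participants, who switch at Week 16, the switch branch prefers values on or before the switch, which protects their Week 16 laboratory values further. Neither rule restores a Week 24 value that has been moved to another window, so the usual effect is a missing Week 24 value for samples outside Days 156-169. On-time samples and those up to 13 days early are kept.
- **The most-extreme and worst-record rules may not matter in practice.** This partly stands. SAP Table 2-3 reports laboratory notables by period, and for the entire treatment period the visit label makes no difference. It could matter for Day 1 to Week 16 if period is derived from the analysis visit, as Section 2.4.1.1 says is done for listings. The worst-record rule matters only if it governs the urinalysis tables. The outputs clearly exposed are the by-visit change and shift summaries in Section 2.7.3.
- **Group 2 windows are contiguous and can be programmed.** True, but they still contradict the stated rule.
- **Closing Week 24 on Day 169 may be deliberate, because dose escalation occurs at Week 24.** The SAP does not say so. Group 1, which includes vital signs, runs to Day 183 and Group 3 to Day 225, and the explanation would not account for Week 16 extending to Day 155. If intended, it is an exception that should be written down.
- **The assessment schedule is not readable.** The laboratory rows and questionnaire marks of Protocol Table 8-1 cannot be read in the supplied text, so which correction applies is open. The contradiction exists under either schedule.

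**Conclusion.** The concern holds and is minor. Group 3 Week 52 overlaps Week 40 by 56 days. If Week 24 is a laboratory visit, the printed Group 2 Week 24 window keeps 14 of the rule's 42 days and none after Day 169; 14 days go to Week 16 and 14 to Week 28.

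The arithmetic mismatch is certain. What remains open is which visits are scheduled for each group and how many samples fall on the affected days, since the documents give no visit timing.

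The Group 1 windows behind the primary endpoint are correct, and so is the Group 3 Week 16 window (86-141) behind SF-36 PCS and ASQoL. SAP Section 2.7 plans no formal safety testing, so the laboratory outputs concerned are descriptive.

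**What to change.** Check both columns against Protocol Table 8-1, then apply the Section 2.4.1.1 rule.

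- **Group 3, Week 40 scheduled:** Week 52 becomes 324-379 (one cell).
- **Group 3, Week 40 not scheduled:** delete the Week 40 cell and set Week 24 to 142-267; Week 52 stays 268-379 (two cells).
- **Group 2, Week 24 scheduled:** Week 16 100-141, Week 24 142-183, Week 28 184-239 (three cells).
- **Group 2, Week 24 not scheduled:** delete the Week 24 cell and set Week 28 to 156-239; Week 16 stays 100-155 (two cells).

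If the redacted Group 3 item has a different schedule from ASQoL and SF-36, give it its own column. If any printed limit is intentional, state the exception beside the rule.

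The cost is three to five table cells, one check against the schedule, and the matching derivation code. No new data are needed.
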